10.3 Assessment of causality

Every effort will be made by the investigator to explain each adverse event and assess its causal relationship, if any, to administration of the study vaccine(s).

The degree of certainty with which an adverse event can be attributed to administration of the study vaccine(s) (or alternative causes, e.g., natural history of the underlying diseases, concomitant therapy, etc.) will be determined by how well the event can be understood in terms of one or more of the following:

• Reaction of similar nature having previously been observed with this type of vaccine and/or formulation.

- The event having often been reported in literature for similar types of vaccines.
- The event being temporally associated with vaccination or reproduced on re-vaccination.

All solicited local (injection site) reactions will be considered causally related to vaccination. Causality of all other adverse events will be assessed by the investigators using the following method:

In your opinion, did the vaccine(s) possibly contribute to the adverse event?

NO : The adverse event is not causally related to administration of the study vaccine(s). There are other, more likely causes and administration of the study vaccine(s) is not suspected to have contributed to the adverse event.

Non-serious and serious adverse events will be evaluated as two distinct events given their different medical nature. If an event meets the criteria to be determined "serious" (see Section 10.5.1 for definition of serious adverse event), the investigator will examine it to the extent to be able to determine ALL contributing factors applicable to each serious adverse event.

Other possible contributing factors include:

- Medical history
- Other medication
- Protocol required procedures
- Lack of efficacy of the vaccine
- Erroneous administration

10.4 Following-up of adverse events and assessment of outcome

Investigators will follow up subjects with serious adverse events until the event has disappeared or until the condition has stabilized regardless of when this occurred in relation to the study conclusion. Investigators will follow up participants with non-serious adverse events until the participant completes the study. Clinically significant laboratory abnormalities, as well as any adverse event, will be followed up until they have returned to normal, or until a satisfactory explanation has been provided. Reports relative to the subsequent course of an adverse event noted for any subject must be submitted to the Study Monitor.

Outcome will be assessed as:

- 1 = Recovered
- 2 = Recovered with sequelae
- 3 = Ongoing at participant study conclusion
- 4 = Died
- 5 = Unknown

YES : There is a reasonable possibility that the vaccine contributed to the adverse event.

10.5 Serious adverse events

10.5.1 Definition of a serious adverse event

A serious adverse event is any untoward medical occurrence that results in death, is life threatening, results in persistent or significant disability/incapacity, requires in-patient hospitalization or prolongation of existing hospitalization or is a congenital anomaly/birth defect in the offspring of a study subject. In addition, important medical events that may jeopardize the patient or may require intervention to prevent one of the other outcomes listed above will be considered serious.

- Life threatening—definition: An adverse event is life threatening if the participant was at risk of death at the time of the event; it does not refer to an event, which hypothetically might have caused death, if it were more severe.
- Disabling/incapacitating—definition: An adverse event is incapacitating or disabling if the event results in a substantial disruption of the participant's ability to carry out normal life functions. This definition is not intended to include experiences of relatively minor medical significance such as headache, nausea, vomiting, diarrhea, influenza, and accidental trauma (e.g. sprained ankle).
- Hospitalization: In general, hospitalization signifies that the participant has been detained (usually involving at least an overnight stay) at the hospital or emergency ward for treatment that would not have been appropriate in the physician's office or outpatient setting.

Hospitalization for either 1) elective surgery related to a pre-existing condition that did not increase in severity or frequency following initiation of the study, or 2) for routine clinical procedures that are not the result of an adverse event, need not be considered as adverse events and are therefore not serious adverse events.

- Routine Clinical Procedure—definition: One which is defined as a procedure which may take place during the study period and will not interfere with the study vaccine administration or any of the ongoing protocol specific procedures.

If anything untoward is reported during an elective procedure, that occurrence must be reported as an adverse event, either 'serious' or 'non-serious' according to the usual criteria.

When in doubt as to whether 'hospitalization' occurred or was necessary, the adverse event will be considered serious.

10.5.2 Reporting serious adverse events

In the event that one or more serious adverse reactions probably or suspected of being related to vaccination are detected following any immunization in any of the vaccine groups, no further vaccinations will be administered until a written report has been submitted to the DSMB, DMID, U.S. Army HSRRB, University of Maryland IRB, FMPOS Ethics Review

Committee and NIAID IRB, and the investigators have conferred with the Local Medical Monitor and SMC.

Any serious adverse events occurring during the study period whether or not considered to be related to the study vaccine/comparator will be reported within 24 hours of the PI being notified to the to the IND sponsor (USAMMDA) at [contact], followed by faxing of the complete AE reporting form to the Sponsor at [contact]. SAEs will also be reported within 24 hours by telephone or E-mail to the Local Medical Monitor, SMC and the FMPOS Ethics Review Committee in Mali. Any SAE that is related to the study vaccine will be reported to GSK-Biologicals within 24 hours of the PI being notified. A written report will follow the initial report within 3 working days. The report will be sent to the Quality Assurance Office, USAMMDA (cf. Appendix 16.3)

Notifications and reports will be provided by USAMMDA to the following agencies by e-mail, fax or telephone within the reporting deadlines required by each agency: the cosponsor (DMID), the DSMB, the University of Maryland School of Medicine IRB, the Food and Drug Administration, the HSRRB, the NIAID IRB, the NIAID DSMB, and GSK-Biologicals. The rationale for USAMMDA serving as the primary contact point for disseminating all SAE reports to these bodies is that communications at the field site are limited, and while every effort will be made to build redundancy into the communications systems, it is possible that phone land lines and E-mail could be down at simultaneously, leaving only satellite phones as a means of communication from Bandiagara. The PI and co-PI on site will make every effort to directly notify all IRBs, sponsors and partners directly within their required reporting deadlines, in addition to the notifications they will receive from USAMMDA.

10.6 Pregnancy

Participants who become pregnant during the study period (up to 30 days after receiving the last vaccine dose) must not receive additional doses of vaccine but may continue other study procedures.

Female participants will be instructed to notify the investigators if they become pregnant at any time during the 12-month study period. Although not considered an adverse event pregnancy will be reported in the same way as an adverse event. All pregnancies occurring during the study period will be followed to term, any premature termination reported, and the health status of the mother and child including date of delivery and the child's gender and weight will be reported to HSRRB with copy to DMID and GSK.

10.7 Treatment of adverse events

Treatment of any adverse event will be provided by the investigators with advice from the Local Medical Monitor. The applied measures will be recorded in the CRF of the participant. The recording of adverse events is an important aspect of study documentation. It is the responsibility of the investigators to document all adverse events according to the detailed guidelines set out. The participants will be instructed to contact the investigators immediately if they manifest any signs or symptoms they perceive as serious.

11 PARTICIPANT COMPLETION AND DROP-OUT

11.1 Definition

From the perspective of data analysis a 'drop-out' is any participant who did not come back for the concluding visit foreseen in the protocol. A participant who returns for the concluding visit foreseen in the protocol is considered to have completed the study.

11.2 Procedure for handling drop-outs

Investigators will attempt to contact those participants who missed scheduled followup visits. Information gathered will be described on the Study conclusion page of the CRF and on Medication/Adverse event forms as appropriate.

11.3 Reasons for drop-out

The Study conclusion page on the CRF will specify which of the following possible reasons were responsible for dropout of the participant from the study:

- Serious adverse event
- Non-serious adverse event
- Protocol violation (to be specified)
- Withdrawal of study consent, not due to an adverse event
- Migration from the study area
- Lost to follow-up
- Other (to be specified)

12 DATA MANAGEMENT AND ANALYSIS

Data entry will be performed on site and in the MRTC/MMVDU data management unit in Bamako if necessary. Data analysis and reporting for primary and secondary endpoints will be done by Statistics Collaborative, Inc., Washington, DC. Data entry and management systems will be 21 CFR Part 11 compliant.

12.1 Primary Endpoints

Occurrence of solicited symptoms during an 8-day follow-up period after vaccination (day of vaccination and days 1, 2, 3 and 7 after vaccination).

Occurrence of unsolicited symptoms during a 31-day follow-up period after vaccination (day of vaccination and 30 subsequent days).

Occurrence of serious adverse events during the study period.

12.2 Secondary Endpoints

Anti-MSP1 antibody titers at time points at which blood samples are collected for serology.

12.3 Study cohorts/datasets to be evaluated

12.3.1 Total cohort

The 'Total Cohort' will include all participants enrolled (defined as randomized to study groups) in the study.

12.3.2 Safety cohort

The 'Safety Cohort' will consist of all participants who have received at least one dose of study vaccine or comparator and for whom any data on safety are available.

The presentation of safety data will explore separately the adverse experiences among participants who received all vaccination, among those who received only some and among those with clinical violations of study protocol.

12.3.3 Immunogenicity cohort

The 'Immunogenicity Cohort' will include all evaluable participants (i.e., those meeting all eligibility criteria, complying with the procedures defined in the protocol, with no elimination criteria during the study) for whom data concerning immunogenicity endpoint measures are available. This will include participants for whom assay results are available for antibodies against at least one study vaccine antigen component after vaccination.

12.4 Estimated sample size

This Phase I trial is not powered to detect differences between groups. Even if comparative statistics for the safety variables will be computed, the study will have low power to detect anything other than very large differences in the incidence of local and general side effects between the vaccination groups. This is done weighing the need to detect any possible untoward reactions against the need to limit the number of volunteers involved for safety purposes. The sample size of 40 is widely accepted and used in industry for the initial assessment of the safety, tolerance and immunogenicity of an investigational vaccine. Incorporation of a comparator vaccine as control will enable broad initial estimates of the incidence of local and general side effects and of immune responses among vaccine recipients.

| Event Rate | Pr 0/20 | Pr 1+/20 |
|------------|---------|----------|
| 0.01 | 0.82 | 0.18 |
| 0.05 | 0.36 | 0.64 |
| 0.08 | 0.19 | 0.81 |
| 0.10 | 0.12 | 0.88 |

Table 4. Event detection probability table.

Event rate. True rate at which an event occurs.

Pr 0/20. Given the event rate, probability that no events will be detected among 20 vaccinees.

Pr 1+/20. Given the event rate, probability that one or more events will be detected among 20 vaccinees.

If the SAE rate is 8%, then the probability of observing at least one event in a group size of 20 (Pr 1+/20) is 0.81. If the SAE rate is 8%, then the probability of observing no event in a group size of 20 (Pr 0/20) is 0.19.

12.5 Final analysis

12.5.1 Analysis of demographics

Demographic characteristics (age, sex and place of residence) of each study cohort will be tabulated. The mean age (plus range and standard deviation) by sex of the enrolled participants, as a whole and per group will be tabulated.

12.5.2 Analysis of immunogenicity

Immunogenicity will be assessed in several ways. A series of graphs will display immunologic responses. For each vaccine group and timepoint, the distribution of anti-MSP-1 antibody levels and reverse cumulative curves will be plotted. Corresponding summary statistics will show means and standard deviations as well as median, 25th and 75th percentiles, and 10th and 90th percentiles. The statistics will be presented both as raw data and as log-transformed data.

In addition, for each treatment group and timepoint, anti-MSP-1 antibody levels will be presented as geometric means of OD units with 95% confidence intervals. For each vaccine group and for each timepoint, a table will show the proportion of volunteers with two-fold, four-fold, and eight-fold increases in anti-MSP-1 antibody titers. To describe more fully the antibody levels over time and to allow more precise estimates of relevant parameters, mixed models will be fit to the observations for individual volunteers and averaged over all volunteers in each vaccine group.

12.5.3 Analysis of safety

The overall percentage of participants with at least one local adverse event (solicited and unsolicited) and the percentage with at least one general adverse event (solicited and unsolicited) during the 8-day follow-up period after vaccination will be tabulated. The incidence, intensity and relationship of individual solicited symptoms over the 8-day follow-up period will be calculated per group and vaccine dose.

The number of participants with at least one report of an unsolicited adverse event, classified by WHO-preferred terms, reported up to 30 days after vaccination will be tabulated per group and vaccine dose. The intensity and relationship to vaccination of the unsolicited symptoms reported will also be assessed.

Serious adverse events are expected to be rare, but where observed will be described. Comparisons of incidence of symptoms, local and general symptoms will be made based on a two-tailed Fischer exact test. Analysis of safety during the 12-month follow-up period will consist of comparison of incidence of serious adverse events as well as hemoglobin, creatinine and ALT levels.

Clinical laboratory parameters

Hematological (CBC) and biochemical (ALT, creatinine) laboratory parameters will be measured at specific time points, Days 0, 14, 30, 44, 60, 74, 90 and starting on day 180 every 3 months. Clinically relevant abnormal values will be tabulated and a trend analysis could be performed if deemed necessary.

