3 SUMMARY

| Title Indication/ Study Population | Double blind randomized controlled Phase I trial to evaluate the safety and immunogenicity of WRAIR's MSP1 candidate malaria vaccine (FMP1) adjuvanted in GlaxoSmithKline Biologicals' AS02A vs. Rabies vaccine in semi-immune adults in Bandiagara, Mali MALARIA-EXPERIENCED ADULTS AGED 18-55 YEARS |
|--|---|
| Principal Investigator | [name]., M.P.H. |
| Rationale | In clinical studies in malaria-naïve adults the FMP1/AS02A was safe and highly immunogenic. A study to evaluate its safety and immunogenicity in malaria-experienced individuals is currently being conducted in Kenya, an area where malaria transmission is intense and perennial. This will be the second study in an endemic area and will evaluate the safety and reactogenicity of the FMP1/AS02A in a population exposed to more limited and seasonal malaria transmission pressure. |
| Objectives | Primary |
| | To evaluate the safety and reactogenicity of WRAIR's MSP1 malaria vaccine (FMP1) adjuvanted in GlaxoSmithKline Biologicals' AS02A in malaria-experienced Malian adults. |
| | Secondary |
| | To evaluate the humoral immune response of WRAIR's MSP1 malaria vaccine (FMP1) adjuvanted in GlaxoSmithKline Biologicals' AS02A in |
| | malaria-experienced Malian adults. |
| Study design | Double blind, randomized, controlled (Imovax® Rabies vaccine) Phase I One study center Study duration: approximately 12 months per subject Immunization schedule: Study days 0, 30 and 60 Route: IM in deltoid muscle |
| Number of subjects | 40 subjects (two groups of 20 each) |
| Co-primary endpoints | • Occurrence of solicited symptoms after each vaccination during an 8- day follow-up period (day of vaccination and days 1, 2, 3 and 7 after vaccination). |
| | • Occurrence of unsolicited symptoms after each vaccination during a 31-day follow-up period (day of vaccination and 30 subsequent days). |
| | • Occurrence of serious adverse events throughout the study period. |
| Secondary endpoint | • Titers of MSP1 antibody at each time point where serology samples are analyzed. |

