6 STUDY DESIGN AND METHODOLOGY

6.1 Overview

- Double blind, randomized controlled phase I study
- One study center
- Screening will be done within 35 days prior to the first immunization
- 40 adults will be randomized in a 1:1 ratio to receive either FMP1/AS02A or Imovax® Rabies vaccine
- Immunization schedule will be on study days 0, 30 ± 7 , and 60 ± 7
- Route of immunization will be deltoid muscle IM
- Data will be collected onto source records and transcribed onto CRFs
- Study duration will be approximately 12 months per participant
- 8-day follow-up (day of vaccination and days 1, 2, 3 and 7 after vaccination) of solicited adverse events
- 31-day follow-up (day of vaccination and 30 subsequent days) of unsolicited adverse events
- Follow-up of serious adverse events (SAEs) until resolution
- Beginning Study Day 120, participants will be visited and assessed by local guides at home at monthly intervals and will be asked to return to clinic every 3 months for safety follow-up.

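### Minor: Fisher's exact test, the only named comparison of symptom incidence, could give way to Boschloo's exact test at no cost, with exact intervals added to serve the stated estimation aim

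*Protocol*

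**What the plan says.** The Summary sets the size as "40 subjects (two groups of 20 each"), and section 6.1 confirms that "40 adults will be randomized in a 1:1 ratio". Section 12.4 states that "This Phase I trial is not powered to detect differences between groups", and adds that "the study will have low power to detect anything other than very large differences in the incidence of local and general side effects". It also says what the design is for: including a comparator "will enable broad initial estimates of the incidence of local and general side effects".

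Section 12.5.3 plans descriptive tables: "The incidence, intensity and relationship of individual solicited symptoms over the 8-day follow-up period will be calculated per group and vaccine dose". It then fixes one inferential method for symptoms: "Comparisons of incidence of symptoms, local and general symptoms will be made based on a two-tailed Fischer exact test". It gives no significance level and names no interval for a safety proportion or a difference. Serious adverse events are to be described, and their 12-month incidence compared by no named method. Section 12.5.2 does name 95% confidence intervals, for antibody geometric means, which are the secondary endpoint. Sections 14.5.2 and 14.6 refer to a separate Report and Analysis Plan, which is not at hand.

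**The concern.** Fisher's test conditions on the total number of participants with the event. With 20 per arm few tables are possible for a given total, so the attainable error rate often falls well below the nominal level. The trial has little power to begin with, and part of the shortfall comes from the choice of test. In a safety comparison the harmful error is to miss a real excess of reactions.

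The second strand is fit to purpose. Section 12.4 speaks of estimating incidence, yet the only inferential output that section 12.5.3 names for symptoms is a p-value. A percentage from 20 people is imprecise, and an interval shows how imprecise.

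**Working it through.** **Inputs.** Arms of 20 and 20 (Summary, section 6.1). Two-tailed Fisher test (section 12.5.3). Significance level: not stated, so two-sided 0.05 is assumed, with 0.01 and 0.10 as a range. Local reactions to rabies vaccine: about 25% (section 4.3.7). The other rates are illustrative assumptions. Dose attrition: 37 of 40 received dose 3 in the Kenyan trial (section 4.3.4), so per-dose tables need not be 20 against 20.

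**The protocol's own figure.** Table 4 is 1 − (1 − r)^20. For r = 0.01, 0.05, 0.08 and 0.10 this gives 0.182, 0.642, 0.811 and 0.878. The printed 0.18, 0.64, 0.81 and 0.88 are reproduced.

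**True size of the tests.** Let F(a,b) be the two-sided Fisher p-value for a and b events. The size at a common rate p is the sum, over all 21 × 21 tables with F(a,b) ≤ 0.05, of Bin(a; 20, p) × Bin(b; 20, p). It was maximised over p = 0.001 to 0.999.

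- Fisher, 20 v 20: maximum 2.53%. At common rates of 5%, 10%, 25% and 50% it is 0.19%, 1.18%, 2.35% and 2.04%.
- Fisher at other nominal levels, 20 v 20: 0.46% at 0.01 and 5.33% at 0.10.
- Fisher at 0.05 with losses: 19 v 19 gives 2.83%, 19 v 20 gives 3.61%, 18 v 20 gives 3.49%, 17 v 20 gives 4.00%.
- Boschloo at 0.05, 20 v 20: maximum 4.64%.

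Boschloo's p-value is the maximum over p of Pr(F ≤ observed F). Fisher's test is valid, so that maximum cannot exceed the observed F. Every table that Fisher rejects is therefore also rejected by Boschloo.

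**Power at 20 v 20, two-sided 0.05** (same sum, with a different rate in each arm):

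| True rates | Fisher | Boschloo | Gain (points) |
|---|---|---|---|
| 25% v 65% | 61.4% | 71.0% | 9.6 |
| 25% v 60% | 49.3% | 58.7% | 9.4 |
| 25% v 50% | 26.9% | 34.1% | 7.2 |
| 10% v 40% | 49.2% | 60.9% | 11.7 |
| 5% v 35% | 58.9% | 69.1% | 10.2 |
| 5% v 25% | 29.9% | 37.6% | 7.7 |

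Repeating these six contrasts at 17, 18 and 19 against 20, with either arm the smaller, gives gains from 0 to about 9 points. Each is smaller than its counterpart at 20 v 20.

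**One table by hand.** Take 5/20 v 12/20, 17 events in all. The lower tail is the sum over x = 0 to 5 of C(20,x) × C(20,17−x), divided by C(40,17): 2,375,853,480 / 88,732,378,800 = 0.02678. Doubling, which is exact for equal arms, gives Fisher p = 0.054. Boschloo gives 0.030. Similarly 2/20 v 8/20 gives 0.065 against 0.039, and 1/20 v 6/20 gives 0.091 against 0.046.

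**Intervals.** Clopper-Pearson for 0/20: upper limit 1 − 0.025^(1/20) = 1 − 0.8316 = 16.8%. For 5/20 the limits are 8.7% and 49.1%; for 10/20 they are 27.2% and 72.8%. As an approximate illustration, the Newcombe 95% interval for 12/20 minus 5/20 is +4.4 to +57.8 points, and for 10/20 minus 5/20 it is −4.7 to +49.4 points.

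**The case against.** The strongest reply is that nothing here is wrong. Fisher's test is valid and conventional for sparse tables, and a size below nominal is a known property. The protocol says twice, in sections 4.3.8 and 12.4, that only very large differences can be detected. That stands: the point is an improvement and not a correction.

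Several stronger readings are tempting, and the documents do not support them.

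- A reader might infer that the safety analysis consists of a p-value alone. It does not. Section 12.5.3 tabulates incidence, intensity and relationship by group and dose, section 12.3.2 adds displays by vaccination completeness, and serious adverse events are not tied to Fisher's test.
- A reader might infer that sections 12.4 and 12.5.3 contradict each other. Tabulated incidences are estimates, and section 12.4 expressly foresees comparative statistics of low power.
- A reader might infer that intervals have been left out. Interval methods commonly sit in an analysis plan, and one is foreseen. Naming intervals for antibody means does not exclude them for safety.
- A reader might infer that a non-significant result will be taken as equivalence to rabies vaccine. No section sets such a rule. Under section 14.4 progression between doses rests on review of accumulated safety data.
- A reader might take 2.5% as a fixed ceiling. It depends on an assumed level of 0.05 and exactly 20 evaluable per arm.

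Table 4 also already warns that zero events does not exclude an appreciable rate: at a true rate of 8%, none would be seen with probability 0.19.

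**Conclusion.** The point holds as a minor, cost-free improvement. The protocol itself fixes the test, so the choice belongs in this document. At an assumed two-sided 0.05, Fisher's test runs at about half its nominal size with 20 per arm, and somewhat closer to nominal when a few participants are missing. Boschloo's test recovers about 7 to 12 points of power at 20 v 20 under the same guarantee, and less with unequal arms.

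The limits matter. Power for moderate contrasts stays low under either test: 34% at best for 25% v 50%. For rare events the change does little: at a common rate of 5% Boschloo's size is 0.21% against 0.19% for Fisher. There the intervals are the more useful part of the change, and whether they are already planned cannot be judged without the Report and Analysis Plan.

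**What to change.** In section 12.5.3, wherever a p-value for symptom incidence is given, replace Fisher's test by Boschloo's exact unconditional test and state the significance level. Specify the two-sided form that orders tables by the two-sided Fisher p-value. The guarantee of never being less powerful than Fisher's test was shown above for that form, and some software instead doubles a one-sided value, which can differ when arms are unequal.

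To serve the aim in section 12.4, present each arm's incidence with a Clopper-Pearson 95% interval and each between-arm risk difference with an exact unconditional 95% interval, unless the Report and Analysis Plan already does so. Optionally, note beside Table 4 that 0/20 has an exact two-sided 95% upper limit of 16.8%.

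The cost is analysis wording and standard software. No participants, visits or samples are added.
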